APPENDIX 6: AMENDMENT HISTORY

Amend-ment No.	Protocol Ver-sion No.	Date issued	Author(s) of changes	Details of Changes made
NA	NA	NA	NA	NA

1. BACKGROUND

Parenteral artesunate is the first-line treatment for severe malaria.^{1,2} The two largest ever treatment trials conducted in patients hospitalised with severe malaria, which compared parenteral artesunate (produced by Guilin/ Fosun) with quinine: SEAQUAMAT in Asia in 1,461 patients³, and AQUAMAT in Africa in 5,425 children⁴. In both trials artesunate was associated with a significant and substantial reduction in mortality compared to quinine (a 34.7% relative reduction in deaths in SEAQUAMAT, 22.5% in AQUAMAT), which was not at the expense of an increase in severe sequelae. These findings resulted in a change of the WHO recommended first line antimalarial therapy for severe malaria in all endemic settings, and it has been estimated by the Medicines for Malaria Venture that since 2011 this has saved well over 500,000 young lives in Africa (<https://www.mmv.org/our-impact/achievements/168-million-vials-artesun-delivered-treat-children-severe-malaria>).

The conventional formulation of injectable artesunate requires a 2-step reconstitution and dilution of the artesunate hemisuccinate powder, including reconstitution in a sodium bicarbonate solution followed by further dilution in 5% dextrose or normal saline. The 2-step procedure takes time and is error prone, dissolving the artesunate powder in the bicarbonate solution is sometimes difficult, and the 2-step procedure requires additional consumables, like sterile syringes (<https://www.severemalaria.org/toolkits-training/injectable-artesunate-tools-training>). Preparation of conventional injectable artesunate (Artesun SmPC) requires shaking the vial for 3 to 5 minutes

STATISTICAL ANALYSIS PLAN

to mix well until the powder is completely dissolved and the solution is clear. Another disadvantage of the conventional artesunate is the two steps needed to reconstitute artesunate powder by sodium bicarbonate first then to dilute the solution by sodium chloride should not be exchanged. Otherwise, artesunate will not be dissolved. Such malpractice can cause a waste of medicine and put critical ill severe malaria patient under risk. 1-step artesunate can avoid such mistakes.

2. GENERAL ANALYSIS APPROACH

The principle of intention to treat (ITT) will be the main strategy of analysis for the primary outcome. These analyses will be conducted on all patients assigned to the treatment groups as randomised. Any patients subsequently found not to be eligible during the trial or that did not receive a full course of study drug will be included in these analyses. Per Protocol (PP) analysis will be conducted to examine robustness of ITT results. This will be a form of sensitivity analysis to the intention to treatment analysis principle. In the PP analyses, all patients wrongly included in the study based on the inclusion/exclusion criteria will be excluded from analyses.

The cost analysis of 1-step parenteral AS will assess health facility-level costs, and health system costs to encompass all costs of a potential change from conventional to 1-step artesunate, including re-training, materials, drug replacement. Unit costs will be assigned to healthcare worker time spent on managing patients with severe malaria (derived from the time and motion surveys). Micro costing will be carried out in each of the sites to estimate the costs of equipment and consumables associated with provision of artesunate with each of the formulations. The resulting labour and consumable mean costs will be compared in patients treated with 1-step vs conventional artesunate formulation.

Time from opening box to completed preparation of syringe will be summarised using means and standard deviation for each each arm. Difference in means and the correponding 95% confidence intervals will be reported. We will provide overall comparisons by arm as well as for each site separately. The comparisons will be done for baseline times ans well as for all recorded times. Total cost of consumables in US dollars will be summarised in a similar way. A Student's independent t-test will be used for comparison of means between groups. The Central Limit Theorem justifies the use of the Student's t-test even if the times/costs may not be normally distributed because of the large sample size. However, if the data will be highly skewed, non-parametric tests such as Manny-Whitney (Wilcoxon) U test will be considered. Statistical significance will be declared at 5% significance level.

Data analysis will be performed using Stata 17 or higher, StataCorp, 4905 Lakeway Drive College Station, Texas 77845 USA

1.1 Data integrity

This study will be conducted in compliance with the protocol, relevant Standard Operating Procedures (SOPs), Good Clinical Practice (GCP) and the applicable regulatory requirement(s). All the analyses will be performed on clean data only.

STATISTICAL ANALYSIS PLAN

1.2 Data cleaning and verification

All data will be cleaned and verified prior to statistical analysis. The study site will be monitored remotely at times agreed on with the Investigator. At the time of each monitoring session, the Monitor will review the completed CRFs to ascertain that all items have been completed and that the data provided are accurate and obtained in the manner specified in the protocol. The Monitor will also check that the data in the CRF are consistent with the clinical records (Source Data Verification [SDV]) and that study results are recorded completely and correctly. The data manager will ensure that clean data is submitted to the statistician for analysis. The statistician will cross-check that the available data for analysis is clean. Any data cleaning queries will need to be resolved before statistical analyses.

1.3 Locking the dataset

After data cleaning and responding to all data queries, the clean data will be locked normally in the database that was used for data capturing. The data may also be locked and stored in other user-friendly formats such as MS Excel and Stata. The locked data will be stored at an identifiable secure place and should be available to the relevant researchers upon request following proper request procedures. The data will also be in other robust backup media.

1.4 Data format and Analysis logs

Prior to dispensing data to the trial statistician, the head of data management will make sure that the data to be sent to the trial statistician is clean. This will help the statistician to provide the analysis results in a timely manner as there will be a reduced amount of queries if clean data is provided to the trial statistician. Data will be given to the Trial Statistician by the head of Data Management (or designated person) in a format that is compatible with statistical software reading. Statistical analyses will be performed in Stata, version 17 or higher, or in R software. Statistical programs and output logs will be kept for all analysis and made available upon request.

1.5 Interim analyses

The interim reports will be upon request by the DSMB. No stopping rules both statistical as well as clinical will be specified. The need to stop the trial will be based on the perception of the accumulating data by the DSMB.

2. Study objectives and endpoints

2.1.1. Primary objective

Assessment of:

1. Convenience and rapidness of administration of 1-step vs. conventional 2-step parenteral artesunate formulations
and
2. Costs of administration of 1-step vs. conventional 2-step parenteral artesunate formulations

STATISTICAL ANALYSIS PLAN

2.1.2. Primary endpoint

1. Time to administration of treatment comparing 1-step vs. conventional 2-step parenteral artesunate formulations (by time-and-motion methods).

and

2. Costs of administration of 1-step vs. conventional 2-step parenteral artesunate formulations at health facility, and at health system level.

2.1.3. Secondary objectives and endpoints

1. To assess and compare *P. falciparum* parasite clearance rates of 1-step vs. conventional 2-step parenteral artesunate formulations.

Parasite clearance half-life and other parasite clearance parameters (PC50, PC90, 12-hour parasite reduction ratio) compared between 1-step vs. conventional 2-step parenteral artesunate formulations.

2. To assess and compare time from intravenous treatment to follow up treatment with oral drugs with 1-step vs. conventional 2-step parenteral artesunate formulations.

Time from start parenteral treatment to follow up treatment with an oral ACT (recovery to per os treatment) of 1-step vs. conventional 2-step parenteral artesunate formulations.

3. To assess and compare disease outcome parameters between 1-step vs. conventional parenteral artesunate formulations.

Fever clearance time (i.e. the time taken for the tympanic temperature to fall below 37.5 °C and remain there for at least 24 hours) of 1-step vs. conventional 2-step parenteral artesunate formulations.

4. To assess and compare adverse events between 1-step vs. conventional 2-step parenteral artesunate formulations

Incidence of adverse events and serious adverse events by study arms within the first 28 days.

STATISTICAL ANALYSIS PLAN

2.2.1 Determination of sample size

Sample size calculations for non-inferiority study is based on dissolution test data from Guilin Pharmaceutical Co. Ltd. ("Study report on the solubility of artesunate for injection (60mg), Doc. RR-QC-ZSYQHHZ (60mg)RJX-2021 30th April 2021).²³ This is supported by unpublished in-house experience (from a bioequivalence study in healthy volunteers, personal communication, [name], Mahidol University) that the conventional formulation takes about 4 minutes with a standard deviation of 2 minutes to administer injectable artesunate. Our non-inferiority margin is 1 minute of drug re-constitution for the new simpler artesunate formulation i.e. if participants in the 1-step artesunate formulation will have a mean of the time of 5 minutes or less of drug re-constitution, with a standard deviation of 2 minutes, then the new formulation will be considered to be non-inferior to the old formulation. With this non-inferiority margin, detecting non-inferiority with 90% power and with a one-sided alpha of 0.025, we will need to recruit 85 participants in the new formulation and 85 in the old formulation arm giving a total of 170 participants. In order to compensate for a 15% loss to follow-up or withdrawal, we will need 100 participants in each arm giving a total of 200 participants in the two arms combined. These calculations were performed in Stata 16 (StataCorp LLC Software).

The sample size calculation dovetails with pragmatic needs for the other study activities the 200 participants provides sufficient variability of participant characteristics to allow staff to gain experience of using 1-step artesunate and be able to provide an informed opinion of its pros and cons. Recruitment of 100 patients per site is feasible over 12 months based on the expected numbers of cases of severe malaria ([name] and [name], personal communication April 2021). The sample size calculation is based only on the time-to-treatment of participants and not on the costing analysis.

STATISTICAL ANALYSIS PLAN

3. Data Analysis

3.1 Trial Profile

The number of patients who will be screened, reasons for non-enrolment, number of patients randomized, number of patients lost to follow up and the number of patients assessed for 28-day endpoints will be summarised in a CONSORT flow diagram, figure 2, below.

[figure not shown]

Figure 2 Consort Trial Profile by Arms

STATISTICAL ANALYSIS PLAN

3.2 Demographics and other baseline characteristics

The following baseline characteristics will be described by study arm in table 1 (below). Variables such as age, heart rate, respiratory rate will be summarized using median and interquartile range. Continuous variables such as weight, height, systolic and diastolic blood pressure, , haemoglobin will be summarized using mean \pm standard deviation. Parasitaemia at baseline will be described as geometric mean and range. Categorical variables such as sex, presence of fever and gametocytaemia at baseline will be summarized using frequencies and percentages.

Table 1. Baseline Characteristics of the Patients

Characteristics	1-STEP AS (N=XXX)	2-STEP AS (N=XXX)	Total (N=XXX)
Age (years), med (IQR)	XX.X (XX.X-XX.X)	XX.X (XX.X-XX.X)	XX.X (XX.X-XX.X)
Male sex, n (%)	XX (XX.X)	XX (XX.X)	XX (XX.X)
Weight (kg), mean (SD)	XX.X (XX.X)	XX.X (XX.X)	XX.X (XX.X)
Height (cm) mean (SD)	XX.X (XX.X)	XX.X (XX.X)	XX.X (XX.X)
Hb (g/dL), mean (SD)	XX.X (XX.X)	XX.X (XX.X)	XX.X (XX.X)
Parasites/ μ L, geometric mean (range)	XX.X (XX.X-XX.X)	XX.X (XX.X-XX.X)	XX.X (XX.X-XX.X)
Impaired consciousness or unrousable coma, n (%)	XX (XX.X)	XX (XX.X)	XX (XX.X)
Prostration, n (%)	XX (XX.X)	XX (XX.X)	XX (XX.X)
Failure to feed and drink without assistance, n (%)	XX (XX.X)	XX (XX.X)	XX (XX.X)
Multiple convulsions, n (%)	XX (XX.X)	XX (XX.X)	XX (XX.X)
Deep breathing, respiratory distress, n (%)	XX (XX.X)	XX (XX.X)	XX (XX.X)
Circulatory collapse or shock, systolic BP < 70 mmHg, n (%)	XX (XX.X)	XX (XX.X)	XX (XX.X)
Clinical jaundice plus evidence of other vital organ dysfunction, n (%)	XX (XX.X)	XX (XX.X)	XX (XX.X)
Haemoglobinuria, n (%)	XX (XX.X)	XX (XX.X)	XX (XX.X)
Suspected pulmonary oedema, n (%)	XX (XX.X)	XX (XX.X)	XX (XX.X)

STATISTICAL ANALYSIS PLAN

Renal failure (< 20 ml urine per hour) , n (%)	XX (XX.X)	XX (XX.X)	XX (XX.X)
Spontaneous bleeding/disseminated intravascular coagulation, n (%)	XX (XX.X)	XX (XX.X)	XX (XX.X)
Several episodes of vomiting in the preceding 24 hrs, n (%)	XX (XX.X)	XX (XX.X)	XX (XX.X)
Severe pallor with respiratory distress OR HCT<15% OR hb<5.0g/dl, n (%)	XX (XX.X)	XX (XX.X)	XX (XX.X)

3.3 Convenience and rapidness of administration of 1-step vs. conventional 2-step parenteral artesunate formulations and Costs of administration of 1-step vs. conventional 2-step parenteral artesunate formulations
Primary objective

To assess:

1. Convenience and rapidness of administration of 1-step vs. conventional 2-step parenteral artesunate formulations
and
2. Costs of administration of 1-step vs. conventional 2-step parenteral artesunate formulations

Primary endpoint

1. Time to administration of treatment comparing 1-step vs. conventional 2-step parenteral artesunate formulations (by time-and-motion methods).
and
2. Costs of administration of 1-step vs. conventional 2-step parenteral artesunate formulations at health facility, and at health system level.

STATISTICAL ANALYSIS PLAN

Table 2 Drug preparation times

Time from opening box to completed preparation of syringe, at baseline only				
	Minutes and seconds, mean (SD)		Difference in means, (95% CI)	p-value
	1-STEP AS (N=XXX)	2-STEP AS (N=XXX)		
Overall	XX.X (XX.X)	XX.X (XX.X)	XX.X (XX.X - XX.X)	X.XXX
By site				
DRC	XX.X (XX.X)	XX.X (XX.X)	XX.X (XX.X - XX.X)	X.XXX
Tanzania	XX.X (XX.X)	XX.X (XX.X)	XX.X (XX.X - XX.X)	X.XXX
Time from opening box to completed preparation of syringe, at all recorded times.				
Overall	XX.X (XX.X)	XX.X (XX.X)	XX.X (XX.X - XX.X)	X.XXX
By site				
DRC	XX.X (XX.X)	XX.X (XX.X)	XX.X (XX.X - XX.X)	X.XXX
Tanzania	XX.X (XX.X)	XX.X (XX.X)	XX.X (XX.X - XX.X)	X.XXX
Total cost of consumables in US dollars, mean, SD.				
Overall	XX.X (XX.X)	XX.X (XX.X)	XX.X (XX.X - XX.X)	X.XXX
By site				
DRC	XX.X (XX.X)	XX.X (XX.X)	XX.X (XX.X - XX.X)	X.XXX
Tanzania	XX.X (XX.X)	XX.X (XX.X)	XX.X (XX.X - XX.X)	X.XXX

USD calculated from average cost of consumables used, and wastage of drug.

STATISTICAL ANALYSIS PLAN

3.4 Fever clearance and parasite clearance during treatment, by treatment allocation

Table 4 Clinical recovery*, fever clearance, and parasite clearance by study arm**

	1-STEP AS N=XXX	2-STEP AS N=XXX	Both groups N=XXX	P- value (2-sided)
Hours to fever clearance, mean (SD) (baseline to start of first 24h period <37.5C; temperature was recorded every 4 hours, until day 2, then 6 hourly)				
DRC	XX.X (X.X)	XX.X (X.X)	XX.X (X.X)	X.XXX
Tanzania	XX.X (X.X)	XX.X (X.X)	XX.X (X.X)	X.XXX
All study sites	XX.X (X.X)	XX.X (X.X)	XX.X (X.X)	X.XXX
Day 3 blood smear still positive, n/N (%)** (taking prior clearance or discharge as negative)				
DRC	XX/XXX (XX)	XX/XXX (XX)	XX/XXX (XX)	X.XXX
Tanzania	XX/XXX (XX)	XX/XXX (XX)	XX/XXX (XX)	X.XXX
All study sites	XX/XXX (XX)	XX/XXX (XX)	XX/XXX (XX)	X.XXX
Hours to tolerate oral medication, mean (SD)* (baseline to start of oral ACT)				
DRC	XX/XXX (XX)	XX/XXX (XX)	XX/XXX (XX)	X.XXX
Tanzania	XX/XXX (XX)	XX/XXX (XX)	XX/XXX (XX)	X.XXX
All study sites	XX/XXX (XX)	XX/XXX (XX)	XX/XXX (XX)	X.XXX
Parasite clearance half-life in hours, mean (SD)** (excluding patients with initial count insufficient to estimate half-life)				
DRC	X.X (X.X)	X.X (X.X)	X.X (X.X)	X.XXX
Tanzania	X.X (X.X)	X.X (X.X)	X.X (X.X)	X.XXX
All study sites	X.X (X.X)	X.X (X.X)	X.X (X.X)	X.XXX

*Protocol recommends patients receive a minimum of 3 doses of injectable artesunate before switch to oral ACT. Patients may vary if discharged before 24 hours, died, or referred.

** Parasite dynamics will be affected by patients who are transfused.

STATISTICAL ANALYSIS PLAN
3.5 Safety assessments and tolerability (Incidence of adverse events and serious adverse events by study arms within the first 28 days)

Safety analyses will be based on the whole population that get administered the study drug. That is, the safety and tolerability data will be pooled from all the sites that received the same antimalarial treatment.

The safety and tolerability of 1-STEP AS versus 2-STEP AS will be assessed by comparing the frequency (%) of adverse events and serious adverse events, with particular attention to the variables listed below, which pertain to severe malaria.

Safety data will be presented in tabular and/or graphical format and summarized descriptively. Any clinically relevant abnormalities or values of potential clinically concern will be described. Patients will be analysed following the intention to treat analysis. All adverse event summaries will refer to treatment emergent adverse events, i.e. adverse events that newly started or increased in intensity after the study drug administration. Adverse events will be graded according to Common Terminology Criteria for Adverse Events (CTCAE). The safety and tolerability summaries will be presented in table 5.

Table 5 Incidence of adverse events within first 28 days by study arm

	1-STEP AS	2-STEP AS	p-value
Number of subjects	XX	XX	
Serious adverse events (SAEs), n/N, (%)	XX	XX	X.XXX
Possible, probable or definite drug related SAEs, n/N, (%)	X/XX (X.X)	X/XX (X.X)	X.XXX
Neurological sequelae at discharge	X/XX (X.X)	X/XX (X.X)	X.XXX
Neurological sequelae at 28	X/XX (X.X)	X/XX (X.X)	X.XXX
Neurological sequelae persisting at end of follow up	X/XX (X.X)	X/XX (X.X)	X.XXX
Grading of adverse events, n/N, (%)	1-2	3-4	1-2
Symptoms			
Impaired consciousness or unrousable coma, n (%)	X/XX (X.X)	X/XX (X.X)	X/XX (X.X)
Prostration, n (%)	X/XX (X.X)	X/XX (X.X)	X/XX (X.X)
Failure to feed and drink without assistance, n (%)			
Multiple convulsions, n (%)			
Deep breathing, respiratory distress, n (%)	X/XX (X.X)	X/XX (X.X)	X/XX (X.X)
Circulatory collapse or shock, systolic BP < 70 mmHg, n (%)	X/XX (X.X)	X/XX (X.X)	X/XX (X.X)
Clinical jaundice plus evidence of other vital organ dysfunction, n (%)	X/XX (X.X)	X/XX (X.X)	X/XX (X.X)
Haemoglobinuria, n (%)	X/XX (X.X)	X/XX (X.X)	X/XX (X.X)
Suspected pulmonary oedema, n (%)	X/XX (X.X)	X/XX (X.X)	X/XX (X.X)

STATISTICAL ANALYSIS PLAN

	X/XX (X.X)	X/XX (X.X)	X/XX (X.X)	X/XX (X.X)	X.XXX
Renal failure (< 20 ml urine per hour) , n (%)	X/XX (X.X)	X/XX (X.X)	X/XX (X.X)	X/XX (X.X)	X.XXX
Spontaneous bleeding/disseminated intravascular coagulation, n (%)	X/XX (X.X)	X/XX (X.X)	X/XX (X.X)	X/XX (X.X)	X.XXX
Several episodes of vomiting in the preceding 24 hrs, n (%)	X/XX (X.X)	X/XX (X.X)	X/XX (X.X)	X/XX (X.X)	X.XXX
Severe pallor with respiratory distress OR HCT<15% OR hb<5.0g/dl, n (%)	X/XX (X.X)	X/XX (X.X)	X/XX (X.X)	X/XX (X.X)	X.XXX
Total	X/XX (X.X)	X/XX (X.X)	X/XX (X.X)	X/XX (X.X)	X.XXX
Laboratory abnormalities					
Creatinine	X/XX (X.X)	X/XX (X.X)	X/XX (X.X)	X/XX (X.X)	X.XXX
Total bilirubin	X/XX (X.X)	X/XX (X.X)	X/XX (X.X)	X/XX (X.X)	X.XXX
Direct bilirubin	X/XX (X.X)	X/XX (X.X)	X/XX (X.X)	X/XX (X.X)	X.XXX
Alanyl transfarase (ALT)	X/XX (X.X)	X/XX (X.X)	X/XX (X.X)	X/XX (X.X)	X.XXX
Aspartate transfarase (AST)	X/XX (X.X)	X/XX (X.X)	X/XX (X.X)	X/XX (X.X)	X.XXX
Alkaline phosphatase	X/XX (X.X)	X/XX (X.X)	X/XX (X.X)	X/XX (X.X)	X.XXX
Hematocrit decrease	X/XX (X.X)	X/XX (X.X)	X/XX (X.X)	X/XX (X.X)	X.XXX

Adverse event grading: grade1 to grade 5 (CTCAE)

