3.2 Study Rationale

We seek to evaluate the practical benefits of the new formulation in a clinical trial supported by an ancillary social sciences study, and a cost analysis informed by the first two activities. The randomised study will formally compare between the two artesunate formulations: the speed and convenience of preparation and use, the costs of drug administration, basic pharmacodynamic measures and adverse events. A mixed method social science study will explore the opinion of healthcare workers regarding the use of the new artesunate formulation, including the policy and implementation perspectives from policymakers. Previous comparisons of artesunate suppositories and parenteral artesunate have reported parasite clearance times⁷ (<https://www.severemalaria.org>), and although both arms of the trial contain an identical active drug (artesunate) in the same dosages, we will also collect this information as a precaution to exclude the possibility of an unexpected, substantial difference in drug activity in patients with severe malaria.⁸

A feasibility assessment of injectable AS is important.⁹ Previous analyses have shown the mortality benefit and cost-effectiveness of reduced delays to effective treatment for severe malaria.^{10,11} Studies to evaluate new treatments for severe malaria should not only rely on efficacy (mortality) outcomes, but also include factors determining effectiveness under field conditions.¹² An important factor is the convenience to use the antimalarial drug. An objective measure of this is the time needed to correctly prepare the artesunate solution for injection, which will be evaluated in this study. In

addition, social science studies will explore the practicalities such as convenience, policy and implementation related issues and perceived benefits of using the new 1-step formulation compared to the conventional 2-step formulation.

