5.5.2. Inclusion criteria

Part 1:

- Male and female children aged >3months and <16 years.
- Clinical diagnosis of severe *P. falciparum* malaria; or parasitological confirmed *P. falciparum* hyperparasitaemia >350,000/ uL.
- Positive malaria test result, by rapid diagnostic test RDT.
- Weight of 5 kg or greater.
- Written informed consent by the parent or guardian.

Part 2:

Study staff and health staff

- Study staff who prepare and administer Artesunate injection to patients in the study or health staff who have not administer the Artesunate injection to patients in the study by themselves

but are either aware of malaria treatment, Artesunate injection, or have observed the treatment provided to severe malaria patients.

- Written informed consent by the study staff and health staff

Study staff for a short video-record

- Study staff who would like to participate in the video record of a procedure to show how 1-step and 2-step Artesunate injections are prepared and administered.
- Written informed consent by the study staff

Policymakers and stakeholders

- Those who are working in the National Malaria Control Program (NMCP) or relevant organizations (WHO, INGOs/NGOs) within the country.
- Written informed consent by the potential participant

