6.6. Blood sampling

6.6.1. On admission (time 0)

Patients will have an intravenous catheter inserted for at least the first 24 hours. An SOP will be provided instructing how this is to be done and how to take blood for protocol tests.

On study admission, immediately before drug administration, blood will be collected according to appendix 3 for the following:

- Parasite count (thick and thin films) and Hct.
- Haemoglobin
- Full blood count
- Reticulocyte count (EDTA-anticoagulated)
- Biochemistry assessments including bilirubin, ALT, AST, Alkaline Phosphatase, and creatinine levels, LDH and any other tests that might be deemed relevant by the treating physician.

Blood glucose In this study patients will be enrolled based on clinical signs of severity and the results of the Rapid Diagnostic Test for reasons of administering the treatment for severe malaria as soon as possible, as the microscopy results are not available before 1 hour. In the case the slides from screening and admission are negative the treating physician will review the diagnosis and change the patient management accordingly. The patient will however be retained in the study (intention to treat).

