In patients presenting with symptoms compatible with severe malaria, the diagnosis should be confirmed by a peripheral blood slide, or by rapid test based on the detection of the malaria antigen HRP2 (e.g., Paracheck-F test). The sensitivity of these rapid antigen test is high (97%), meaning that a negative test almost excludes the diagnosis *falciparum* malaria. However, the specificity depends on the endemicity of the disease, since the test can remain positive for a few weeks after a malaria attack. Especially in highly endemic areas a positive test can thus be caused by a recent malaria episode, whereas the cause of the presenting fever can be a different one. The specificity of the test in non-endemic countries can be as high as 100% but drops to 85% in malaria endemic areas. A positive malaria slide, especially in the adult patient, does not prove that the presenting symptoms are caused by severe malaria, because of the high background prevalence of peripheral blood parasitaemia. Other causes of coma have thus also to be considered, including: hypoglycaemia, meningitis, septic shock and post-ictal coma (after febrile convulsion). Moreover, sedative drugs, severe anaemia, severe acidosis or severe hyponatraemia can contribute. All these factors (except meningitis and sedative drugs) can occur as a complication of severe malaria. Consequently, blood glucose and Haematocrit should be checked in every patient (i-STAT or glucose-stick), a lumbar puncture should be performed, and the blood pressure has to be measured. If available electrolytes and acid-base status should be checked. The treatment of these conditions is described below

Antimalarial treatment

The mainstay of the treatment of severe malaria is the immediate start of parenteral antimalarial treatment. The available antimalarial drugs to treat severe malaria are parenteral quinine and the parenteral artemisinin derivatives (artesunate).

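### SAP Table 4 takes hours to fever clearance without limiting the row to children febrile at baseline, so a child who is never febrile scores 0 h and dilutes the comparison

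*SAP*

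**What the plan says.** **Entry.** Protocol section 5.5.2 asks for "Clinical diagnosis of severe *P. falciparum* malaria; or parasitological confirmed *P. falciparum* hyperparasitaemia >350,000/ uL" and "Positive malaria test result, by rapid diagnostic test RDT". Fever appears nowhere in the list. A slide count is needed only on the hyperparasitaemia-only route. Section 5.5.3 allows earlier oral antimalarials or one pre-referral rectal artesunate dose.

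**Slide-negative children.** Protocol section 6.6.1 says "In the case the slides from screening and admission are negative the treating physician will review the diagnosis and change the patient management accordingly", and then "The patient will however be retained in the study (intention to treat".

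**Fever clearance.** Protocol section 5.4.3 (repeated in SAP 2.1.3) defines it as the time for the temperature to drop under 37.5°C and stay there for 24 hours or more. SAP Table 4 turns this into "Hours to fever clearance, mean (SD) (baseline to start of first 24h period <37.5C". Neither text says what to do with a child who has no fever at the start.

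**Other Table 4 rows.** The day-3 smear row counts children still positive, with earlier clearance or discharge taken as negative. Only the half-life row drops children on a baseline value: those whose initial count is too low to estimate a half-life.

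**Baseline fever.** SAP 3.2 says "Categorical variables such as sex, presence of fever and gametocytaemia at baseline will be summarized using frequencies and percentages", so the variable is expected to be available. Table 4 does not use it.

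**Populations.** SAP section 2 names intention to treat for the primary outcome, and section 3.5 names it for safety. Table 4 states no population.

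**The concern.** A clearance time means something only for a child who has something to clear. The protocol's wording presupposes a febrile start. The SAP's operational rule does not: for a child below 37.5°C throughout, the first qualifying 24-hour period starts at baseline and the time is zero. That zero says nothing about the drug, yet it enters the mean and SD of both arms.

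The per-protocol set would not remove these children. It excludes only those wrongly included against the eligibility criteria, and an afebrile child with severe malaria is correctly included.

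At stake is how the row is read. A diluted difference with a wider SD looks like agreement between the formulations. Fever clearance is the endpoint that the SAP attaches to the disease-outcome objective, and Table 4 prints a two-sided p-value for it, so the row will be taken as evidence on that objective.

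**Working it through.** **The plan's own figure.** The only sample-size calculation is for preparation time: margin 1 minute, SD 2 minutes, one-sided alpha 0.025, power 90%. The normal formula gives 2 × 2² × (1.960 + 1.282)² / 1² = 84.06, so 85 per arm, and 85 / 0.85 = 100 after 15% loss. This reproduces the plan and is not affected here. The plan gives no figure for fever clearance.

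**Inputs for the fever row.** From the plan: 100 children per arm. Assumed, because the documents give none of them: febrile share f of 0.90, 0.80 or 0.60, equal in both arms; among febrile children, means of 24 h and 30 h (a 6 h difference) and SD 16 h; every child afebrile at H0 scores 0 h.

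**Formulas.** With a share f at mean μ and SD s, and the rest at zero:
- expected difference = f × 6
- variance in an arm = f·s² + f(1 − f)·μ²
- SE, all children = √[(variance₁ + variance₂)/100]
- SE, febrile only = √[2 × 16² / (100f)]

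**Example, f = 0.80.** Variances are 0.8 × 256 + 0.16 × 576 = 296.96 and 0.8 × 256 + 0.16 × 900 = 348.80. The SE is √(645.76/100) = 2.54, the difference is 4.8 h, and the expected z is 1.89. In febrile children only, with 80 per arm, the SE is √(512/80) = 2.53, the difference is 6 h, and the expected z is 2.37.

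| Febrile share | Difference, all children | SE | z | Difference, febrile only | SE | z |
|---|---|---|---|---|---|---|
| 0.90 | 5.4 h | 2.44 | 2.22 | 6 h | 2.39 | 2.52 |
| 0.80 | 4.8 h | 2.54 | 1.89 | 6 h | 2.53 | 2.37 |
| 0.60 | 3.6 h | 2.57 | 1.40 | 6 h | 2.92 | 2.05 |

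Under these inputs the restricted comparison is sharper at every share, despite fewer children.

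**Day-3 smear row.** Let s be the share slide-positive at baseline, and assume 10% against 20% of those children are still positive at day 3. Counting everyone gives 10s% against 20s%. At s = 0.80 that is 8% against 16%: the absolute difference falls from 10 to 8 points and the risk ratio stays at 2. Power at two-sided 5% is 42.4% with 80 slide-positive children per arm and 41.3% with all 100. At s = 0.98 it is 50.0% and 49.9%. The choice of denominator changes the printed percentages but hardly the test.

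**The case against.** **The population is not stated.** A reader might infer that Table 4 is computed on all randomised children. The SAP does not say so. Intention to treat is named for the primary outcome and for safety, and the protocol's definition suggests a febrile start. This stands: the literal derivation includes afebrile children, but an analyst could exclude them and still claim to follow the protocol. That ambiguity is itself a reason to write the rule down.

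**Afebrile at H0 is not always 0 h.** A child below 37.5°C at H0 who becomes febrile at H4 or H8 gets a non-zero, informative time. This stands, and makes the table above an upper bound on the dilution.

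**The day-3 row.** It is tempting to say that slide-negative children pull the arms together there too. The absolute difference does shrink, but the risk ratio is unchanged and the test almost so.

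**The number of slide-negative children.** Appendix 4 of the protocol says "The specificity of the test in non-endemic countries can be as high as 100% but drops to 85% in malaria endemic areas". A reader might turn this into an expected count among the 200. The documents do not support that: it needs an assumed prevalence, it equates a false-positive rapid test with a negative slide, and it ignores the clinical judgement of severity that enrolment also requires. The statement shows that such children are foreseeable, not how many there will be.

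**The purpose of the data.** Protocol section 3.2 collects information "as a precaution to exclude the possibility of an unexpected, substantial difference in drug activity in patients with severe malaria". That sentence is about parasite clearance times, not fever, and the half-life row, which serves that purpose most directly, already has a baseline exclusion.

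**Importance.** The protocol calls these outcomes exploratory and unpowered. Randomisation balances afebrile children between arms in expectation, so nothing here favours a formulation.

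**Conclusion.** The point holds for the fever row. The SAP rule, read literally, gives 0 h to a child afebrile from baseline onwards. Including such children reduces the mean difference by up to their share and adds variance. With 10% to 40% afebrile at baseline and all scored 0 h, a true 6 h difference would show as 5.4 h to 3.6 h. The shares, the 6 h, and the mean and SD behind the z values are assumptions; the direction does not depend on them as long as some children score 0 h and any true difference among the others has one sign.

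For the day-3 row the gain is a correct denominator and consistency with the half-life row, not a rescued test.

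This is dilution of one outcome, exploratory in the protocol and secondary in the SAP. It is not bias towards an arm, and the co-primary time and cost endpoints and the sample size are untouched. It is worth settling before analysis because the remedy is a few lines of SAP text.

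**What to change.** In SAP 3.4, Table 4:

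- Compute hours to fever clearance in children with a documented pre-dose temperature of at least 37.5°C at H0. This is the threshold that protocol section 6.5 uses for documented fever.
- Print the n for that row and the number excluded in each arm.
- Keep the all-randomised version as a supporting row, and state that a child afebrile throughout scores 0 h in it.
- Give the day-3 row with children slide-positive at baseline as the denominator, with its own n.

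No new data are needed. Protocol Appendix 3 schedules temperature and a blood film at H0, and section 6.6.1 places the admission sample immediately before dosing. A restriction on pre-dose values cannot be affected by treatment. Slides are read without knowledge of allocation (section 6.3). Temperature is not covered by that safeguard in this open-label trial, which is one more reason to show the exclusions by arm.

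The cost is a smaller n in these rows, and children who first become febrile after H0 appear only in the supporting fever row.
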